4.4.3.3 Individual Stopping Criteria

Dosing will be stopped for an individual patient at any time in the study if:

- A patient experiences a serious or intolerable adverse event (AE) that, in the Investigator's opinion, requires study drug discontinuation.
- A patient experiences a TEAE that is severe in intensity and related to administration of WVE-003 (except TEAEs associated with lumbar puncture).

The patient will be followed up for safety per protocol. Per the Investigator's judgement, the patient may be allowed to resume participation in the study if or when the event has resolved]. Dosing may be resumed for individual patients upon recovery from the severe event and if supported by the Investigator, based on their assessment of the benefit/risk balance for the patient.

4.4.3.4 *Adverse Events That are Exempt from Stopping Criteria*

Intrathecal administration of drugs is known to result in untoward effects such as post-lumbar puncture headache, pain, etc.^{33,34} Given the common occurrence of such side effects following lumbar puncture, it is anticipated that patients may experience AEs temporal to the IT administration procedure that are not attributable to study drug^{33,34}. Therefore, the AE terms listed in [Table 5](#) will be exempted from the assessment of Stopping Criteria:

Table 5 Adverse Event Preferred Terms Exempted From Stopping Criteria

Preferred Terms Exempt From Stopping Criteria	
Administration site bruise	Instillation site bruise
Catheter site bruise	Post-lumbar puncture syndrome
Infusion site bruising	Post-procedural discomfort
Infusion site discomfort	Post-procedural contusion
Infusion site pain	Procedural headache
Injection site bruising	Procedural pain
Injection site discomfort	Traumatic lumbar puncture
Injection site pain	

Abbreviations: AE = adverse event; MedDRA = Medical Dictionary for Regulatory Activities; PT = Preferred Term.

Note: AEs exempted from the Stopping Criteria include the MedDRA PTs listed above and their associated verbatim terms.

While these procedural events are exempt from Stopping Criteria review, they will be recorded as AEs as described in [Section 9](#). In addition, as part of their ongoing review of unblinded safety data, the SMC will carefully review the above-referenced exempted AE terms to ensure there are no meaningful imbalances between treatment groups.

4.4.4 Communication of Emergent Safety Concerns

Enrollment to the study will be closely monitored by the Sponsor. If the stopping criteria are met at any point in the study, enrollment and dosing will be suspended until the data are reviewed by the SMC. Notification of dose suspension for a given cohort will be made in accordance with applicable regulations. If a determination is made to resume the study, information will be submitted to the regulatory authorities in accordance with local regulations (e.g., substantial amendment) prior to restarting treatment. Similarly, if an SAE occurs in the sentinel patients in a cohort, no additional patients will be dosed in that cohort until the safety data are reviewed. The Sponsor and/or contract research organization (CRO) will inform all sites in writing if enrollment and/or dosing is suspended. In addition, if enrollment is suspended, the interactive response technology (IRT) system will be adjusted such that no patients can be randomized to treatment until the safety review has been completed and a decision has been made to resume enrollment/dosing.

4.4.5 Considerations Due to COVID-19 Pandemic

Due to the continuing COVID-19 pandemic, it is possible that modifications to the planned schedules of assessments may be necessary in response to local mandates, site closures, quarantines, travel limitations, etc. In light of the serious and progressive nature of HD and the lack of any alternative treatment options for patients, the Sponsor believes that patients may continue to participate in the study and receive investigational treatment provided that appropriate safety monitoring can be performed to ensure patient safety and protocol requirements can be met to ensure the overall scientific integrity of data collection. The following guidelines should be followed to ensure compliance in situations where trial conduct may need to be modified in response to the COVID-19 pandemic:

Screening Activities: Screening activities may continue as long as local and institutional guidelines permit and if the protocol can be followed using the protocol-allowed visit windows. If this cannot be achieved, sites should temporarily halt screening new patients until local and institutional restrictions have been lifted.

Informed Consent Forms: If the ICF cannot be signed in person due to COVID-19 restrictions, or in the case of re-consent due to study changes, the Investigator may review the ICF via video or phone call to the patient. A copy of the signed ICF should be provided in person at the next clinic visit or by a secure process in accordance with site practices and local regulations. Record of informed consent should be filed in the medical record. If a signed copy of the form cannot be obtained from the patient, the ICF should be reviewed in the presence of an impartial witness (who is with the patient), and a witness attestation should be filed in the medical record. In the event a photograph of the ICF is used, an attestation should be made in the medical record by the person entering the form as to how the photograph was obtained.

Active Study Patients: Study dosing may continue as long as local and institutional guidelines permit, and safety monitoring is possible. If patients cannot be seen in clinic due to shelter-in place orders or institutional guidance, the Investigator should temporarily discontinue

administration of study drug and complete study visits that are amenable to remote or local assessments.

For study visits with assessments that can be performed locally, the Investigator should make every attempt to have a local laboratory perform the tests, or assess whether a home health service is available to collect samples at a patient's home by a trained nurse/phlebotomist.

If patients cannot attend their scheduled dosing visit, it is preferable to administer the missed dose if it can be safely administered at a subsequent time point.

All missed visits or changes to the study visit schedule outside of required visit windows due to COVID-19 should be noted as such in the electronic case report form (eCRF; [Section 15.2.1](#)). In addition, any changes to planned assessments due to the patient not being able to visit the clinic should be recorded as protocol deviations and marked "Due to COVID-19" ([Section 15.3.2](#)).

Vaccination: WVE-003 does not target the immune system, so immune response to COVID-19 vaccination is unlikely to be affected. Similarly, COVID-19 vaccination would not be expected to impact safety or efficacy of WVE-003. Investigators should consider the timing of dosing in the study with regard to timing of vaccination, when possible, so as to minimize the potential to confound interpretation of adverse events.

5 PATIENT SELECTION AND WITHDRAWAL CRITERIA

Approximately 54 patients will be enrolled. Patients will be randomized to a treatment arm/dose group only if they qualify according to all of the following inclusion and exclusion criteria. Patients will be required to be prescreened to determine heterozygosity at SNP3 with the A variant only on the same allele as the CAG triplet expansion.

During Screening, patients who do not meet all remaining inclusion/exclusion criteria will be considered screen failures. Patients who screen fail may be rescreened, as appropriate, in consultation with the Medical Monitor and when approved by the Sponsor.

5.1 Inclusion Criteria

1. Documented ability to understand the written study ICF(s) and consent and has provided signed written informed consent prior to any study procedures
2. Ambulatory male or female
3. Age ≥ 25 to ≤ 60 years old
4. Body mass index $\leq 32 \text{ kg/m}^2$
5. Documented CAG triplet repeats ≥ 36 in the *HTT* gene
6. Documented heterozygosity at SNP3

7. Documented presence of the A variant of SNP3 on the same allele as the pathogenic CAG triplet expansion
8. Clinical diagnostic motor features of HD, defined as UHDRS Diagnostic Confidence Score = 4
9. UHDRS TFC scores ≥ 9 and ≤ 13
10. In the opinion of the Investigator, the patient is able to tolerate all study procedures, and is willing to comply with all other protocol requirements.
11. Willingness to practice highly effective contraception for the duration of the study and for [REDACTED] after the last dose of study drug, if patients or their partners are of childbearing potential. Non-childbearing potential and highly effective methods of contraception are defined in (Section 5.2.1.1 and Section 5.2.1.2). In addition, willingness to forego sperm or ova (egg) donation for the duration of the study and [REDACTED] months after completion of the study.

5.2 Exclusion Criteria

1. Malignancy or received treatment for malignancy, other than treated basal cell or squamous cell carcinoma of the skin, within the previous 5 years
2. Positive for Hepatitis B virus (HBV) or Hepatitis C virus (HCV).
3. Known to be positive for human immunodeficiency virus (HIV).
4. Clinically significant medical finding on the physical examination other than HD that, in the judgment of the Investigator, will make the patient unsuitable for participation in and/or completion of the study procedures
5. Previously received tominersen
6. Received prior treatment with viral or cellular-based gene therapy
7. Received any other study drug, including an investigational oligonucleotide, within the past 1 year or 5 half-lives of the drug, whichever is longer, with the exception of the following:
 - a. Received WVE-120101 within the last 3 months (i.e., 5 half-lives); or
 - b. Received WVE-120102 within the last 3 months (i.e., 5 half-lives)
8. Implantable CNS device that may interfere with ability to administer study drug via lumbar puncture or undergo MRI scan

9. History of substance abuse disorder (except nicotine) within 6 months prior to the Screening Visit
10. Positive for opioids (unprescribed), cocaine, amphetamines, methadone, barbiturates, methamphetamine, or phencyclidine at the Screening Visit
11. Started or changed dose for concomitant medication for the treatment of HD symptoms or psychiatric disorders within 30 days prior to the Screening Visit (concomitant medications that have been administered on a stable regimen for ≥ 30 days are permitted)
12. Pregnant (as determined by a serum pregnancy test) or breast feeding at the Screening Visit, or plans to become pregnant during the course of the study
13. Clinically significant laboratory abnormality at Screening
14. Clinically significant abnormality at Screening ECG, including but not necessarily limited to a confirmed QT interval corrected for heart rate (QTc) ≥ 450 msec for males or ≥ 470 msec for females
15. Clinically significant cardiovascular, endocrine, hepatic, renal, pulmonary, gastrointestinal, neurologic, malignant, metabolic, psychiatric, or other condition that, in the opinion of the Investigator, precludes the patient's safe participation in the study or would interfere with the study assessments. Mental status, psychiatric medical history, and eligibility for the study must be documented in the screening questionnaire.
16. Bone, spine, bleeding, or other disorder that exposes the patient to risk of injury or unsuccessful lumbar puncture
17. Inability to undergo brain MRI (with or without sedation)
18. Deemed to be at significant risk for suicidal behavior based on any the following criteria:
 - a. The opinion of the Investigator
 - b. Answers "yes" to Actual Suicide Attempts or Suicidal Behaviors in the Suicidal Behaviors section of the C-SSRS with reference to a 2-year period prior to the Screening Visit
 - c. Answers "yes" on any items in the Suicidal Ideation section of the C-SSRS with reference to a 6-month period prior to the Screening Visit
 - d. Answers "yes" on any items in the Suicidal Ideation section of the C-SSRS at the Baseline Visit since the last visit (Screening Visit)

19. Involved directly or indirectly in the conduct and administration of this study as an Investigator, sub-investigator, study coordinator, or other study staff member, or the patient is a first-degree family member, significant other, or relative residing with one of the above persons involved directly or indirectly in the study
20. History of hypersensitivity to other antisense oligonucleotides and any other drug that, in the opinion of the Investigator, may preclude study participation.

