
6. Documented heterozygosity at SNP3
 
7. Documented presence of the A variant of SNP3 on the same allele as the pathogenic CAG triplet expansion
 
8. Clinical diagnostic motor features of HD, defined as UHDRS Diagnostic Confidence Score = 4
 
9. UHDRS Total Functional Capacity (TFC) scores ≥ 9 and ≤ 13
 
10. In the opinion of the Investigator, the patient is able to tolerate all study procedures, and is willing to comply with all other protocol requirements.
 
11. Willingness to practice highly effective contraception for the duration of the study and for [REDACTED] [REDACTED] after the last dose of study drug, if patients or their partners are of childbearing potential. Non-childbearing potential and highly effective methods of contraception are defined in the protocol. In addition, willingness to forego sperm or ova (egg) donation for the duration of the study and [REDACTED] months after completion of the study.
 
Exclusion Criteria:
 
1. Malignancy or received treatment for malignancy, other than treated basal cell or squamous cell carcinoma of the skin, within the previous 5 years2. Positive for Hepatitis B virus (HBV) or Hepatitis C virus (HCV).3. Known to be positive for human immunodeficiency virus (HIV).4. Clinically significant medical finding on the physical examination other than HD that, in the judgment of the Investigator, will make the patient unsuitable for participation in and/or completion of the study procedures5. Previously received tominersen6. Received prior treatment with viral or cellular-based gene therapy7. Received any other study drug, including an investigational oligonucleotide, within the past 1 year or 5 half-lives of the drug, whichever is longer, with the exception of the following:
a. Received WVE-120101 within the last 3 months (i.e., 5 half-lives); orb. Received WVE-120102 within the last 3 months (i.e., 5 half-lives)8. Implantable central nervous system device that may interfere with ability to administer study drug via lumbar puncture or undergo MRI scan9. History of substance abuse disorder (except nicotine) within 6 months prior to the Screening Visit10. Positive for opioids (unprescribed), cocaine, amphetamines, methadone, barbiturates, methamphetamine, or phencyclidine at the Screening Visit11. Started or changed dose for concomitant medication for the treatment of HD symptoms or psychiatric disorders within 30 days prior to the Screening Visit (concomitant medications that have been administered on a stable regimen for ≥ 30 days are permitted)12. Pregnant (as determined by a serum pregnancy test) or breast feeding at the Screening Visit, or plans to become pregnant during the course of the study13. Clinically significant laboratory abnormality at Screening14. Clinically significant abnormality at Screening electrocardiogram (ECG), including but not necessarily limited to a confirmed QT interval corrected for heart rate (QTc) ≥ 450 msec for males or ≥ 470 msec for females			

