11.1 Sample Size Determination

The sample size was not calculated on the basis of statistical hypothesis testing; however, the number of patients is sufficient for a Phase 1b/2a assessment of safety, tolerability, PK, and early measures of PD and clinical effects.

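### Exclusion criterion 7 contradicts itself for prior recipients of WVE-120101 and WVE-120102: as worded, a dose in the last 3 months is exempt and one 3 to 12 months ago is excluded

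*Combined protocol and SAP*

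**What the plan says.** Criterion 7 in Section 5.2 opens with a general rule: "Received any other study drug, including an investigational oligonucleotide, within the past 1 year or 5 half-lives of the drug, whichever is longer, with the" and then the exception clause. The clause reads "whichever is longer, with the exception of the following" and leads into two items. Item a is "Received WVE-120101 within the last 3 months (i.e., 5 half-lives); or" and item b is "Received WVE-120102 within the last 3 months (i.e., 5 half-lives", with the bracket closing after it. The exclusion list in the synopsis carries the same criterion in the same words. Nowhere else do the documents mention these two products or state a different rule for them.

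Two other sections show how the protocol treats clearance. Section 5.2.1.2 uses five elimination half-lives as the minimum time that male participants must continue condom use after the last WVE-003 dose. Section 4.1.3.2 requires the Period 1 Week 12 visit before multiple dosing, so that study drug has washed out sufficiently.

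**The concern.** The grammar and the gloss pull in opposite directions. Grammatically, recent receipt of either product is what releases a patient from the exclusion. Yet an interval described as five half-lives is normally the time a patient must wait, not a period during which recent exposure is acceptable. Section 5 requires patients to meet all the criteria before randomization, so sites have to apply this one, and two careful sites could apply it in opposite ways. One could randomize a patient dosed last month. The other could randomize a patient dosed six months ago who fails the literal criterion, which would then be a departure to document under Section 15.3.2.

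The primary objective is safety, and Section 2 already says that separating drug-related from procedure-related events is hard with few patients. Residual exposure to another study drug could add a third possible cause. It could also affect baseline CSF safety and pharmacodynamic values. Section 11.3.3 analyzes change from baseline in the biomarkers without a baseline covariate, so any shift in a patient's baseline would carry straight into that patient's change. The analysis populations in Section 11.2.1 remove nobody for prior exposure. Cohorts are small: P1C3 is planned at 12 patients allocated 2:1 (Section 2.3), so 12 × 2/3 = 8 on active, and one affected active patient would be 1 of 8.

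**Working it through.** The plan gives no figure to reproduce. Section 11.1 says "The sample size was not calculated on the basis of statistical hypothesis testing", and no power or precision calculation depends on this criterion. The check is to apply the criterion at each time since last dose.

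**Inputs, all from criterion 7**
- General window: the longer of 1 year (12 months) and five half-lives.
- Items a and b: 3 months, equated with five half-lives.
- Link between them: an exception to the exclusion.

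**Step 1: general window for these two products.** The implied half-life is 3/5 = 0.6 months, or 0.6 × 30.4375 ≈ 18 days. The general window is max(12, 5 × 0.6) = max(12, 3) = 12 months.

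**Step 2: the two readings.** Let t be months since the last dose of either product.
- Literal reading: excluded if t ≤ 12 and not (t ≤ 3), which is 3 < t ≤ 12.
- Replacement-window reading (items a and b stand in place of the 1-year limit): excluded if t ≤ 3.

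| Time since last dose | Literal reading | Replacement-window reading |
|---|---|---|
| 0 to 3 months | not excluded | excluded |
| more than 3, up to 12 months | excluded | not excluded |
| more than 12 months | not excluded | not excluded |

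**Step 3: comparison.** The readings give opposite answers for every last dose within the past 12 months and agree beyond that. The literal rule also runs allowed, excluded, allowed as time since dosing grows, which no clearance argument would produce.

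**Step 4: consistency with the rest of the protocol.** Sections 5.2.1.2 and 4.1.3.2 both treat elapsed time as the safeguard. An exemption confined to patients still inside five half-lives does not fit that approach. This supports the view that the wording is not what was meant, but it does not tell a site which rule to apply.

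**The case against.** The best reply is that this is loose drafting that any site would understand. Items a and b sit in an exclusion list, are phrased like the other exclusions, and carry a washout gloss, so a reader would naturally take them as a product-specific window replacing the 1-year limit. That is probably the intent, and nothing in the documents shows that anyone applied the literal reading. But the text does not say so, the synopsis repeats the problem, and eligibility should not depend on guessing intent.

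There are partial safeguards. Prior HD treatments (Section 8.2.1) and prior medications with dates (Section 8.2.2) are recorded, so exposed patients should be identifiable. Allocation is randomized, so carry-over would not be systematically directed to one arm, although small cohorts can be imbalanced by chance. These limit the consequence without repairing the rule.

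A reader might infer more than the documents support in three ways:
- **That everyone treated longer ago is shut out.** The literal exclusion ends at 12 months. Nor is excluding washed-out patients up to 1 year peculiar to these products: the general rule takes the longer limit, so it does the same for any drug with a short half-life.
- **That the bias can be sized from the half-life.** With a half-life of about 18 days, first-order decline would leave 0.5^(30/18.3) ≈ 32% of a dose at 30 days. This assumes a single compartment and a 3-month figure that may be rounded, and the protocol does not say whether it refers to plasma or CSF. A residual drug fraction is also not a shift in any endpoint.
- **That baseline mHTT or NfL would be contaminated.** The documents do not describe what the two products are, what they target, or what they do to these markers. The effect is possible but not shown.

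**Conclusion.** The concern holds as an internal contradiction in an operative eligibility rule. For prior recipients of WVE-120101 or WVE-120102, the wording and its gloss give opposite results for any last dose within the past 12 months. The literal reading admits the most recently exposed patients. This conclusion rests only on the text of criterion 7 and the absence of a correcting passage; it needs no assumption about decay.

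The consequences for adverse event attribution and for baseline pharmacodynamic and CSF safety values are possible, but their size is unknown. So is the number of patients affected, which may be zero. No sample size or other statistical figure changes. The point should be fixed because the rule governs entry to a small first-in-human safety study and correcting it is cheap, not because harm has been demonstrated.

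**What to change.** Reconcile criterion 7 in Section 5.2 and in the synopsis so that both state, in one unambiguous sentence, which prior recipients of WVE-120101 and WVE-120102 are excluded. The rule and the interval are for the sponsor to set; none is proposed here.

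From the prior-treatment and prior-medication data already collected under Sections 8.2.1 and 8.2.2, list every enrolled patient with previous WVE-120101 or WVE-120102 dosing and the time since last dose. If the list is empty or shows no recent dosing, nothing more is needed. If any patients were recently dosed, report the safety and pharmacodynamic results with and without them.

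The cost is a wording change in two places and one listing, with no effect on sample size. The sponsor would need to decide whether the rewording counts as a minor clarification or requires submission under Section 15.3.1.
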